Recent literature including our finding from an observational study suggests that cumulative lipid intake may be associated with PNAC in high-risk infants with GI surgical disorders. The side effects of intravenous lipid infusions on the hepato-biliary system was first suggested in animal studies in 1993 when La Scala et al. described that the addition of lipids increases TPN associated cholestasis in rats [18]. Haynes et al. in 2002 published a series of hepatic pathology and described dose dependent hepatic changes with prolonged administration of lipid in premature baboons which included steatosis, cholestasis, and proliferation of bile ducts [19]. Since then few observational studies in neonates have been performed and demonstrated that lipid intake is associated with PNAC. [7, 11] However, a cause and effect relationship between lipid intake and PNAC has not been established using a well-designed randomized clinical trial. We hypothesize that increased cumulative amount of lipid intake causes PNAC in late preterm and term neonates with major GI surgical disorders. Our objective is to evaluate the effect of cumulative amount of lipid intake on the incidence of PNAC in this vulnerable population.

III. CHARACTERISTICS OF THE RESEARCH POPULATION

1. **Number of Subjects:** This is a prospective randomized clinical trial involving 40 neonates with major GI surgical disorders requiring surgery.
2. **Gender, Age, Race, and Ethnicity:** The University of Rochester Medical Center (URMC) is a tertiary care center and consists of a 52 bed Neonatal Intensive Care Unit. Annually, ~25 infants with major GI surgical disorders are admitted to the URMC. The NICU population is approximately 52%

male with a racial distribution of 64% White, 32% African-American, 2% Asian, and 2% other. The ethnic distribution is 75% non-Hispanic. The gender, race, and ethnicity distribution of this prospective study is expected to follow the distribution of the NICU population.

3. **Inclusion Criteria:** All neonates \geq 34 weeks gestational age with major GI surgical disorders (gastroschisis, omphalocele, volvulus, trachea-esophageal fistula, duodenal atresia, jejunal atresia, ileal atresia, hirschsprung's disease, anorectal malformation, intestinal obstruction, and GI perforations) requiring surgery admitted to our NICU within first 72 hours will be eligible for this study.

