- e) Registration:** A log sheet of subjects registered with their names, study ID numbers, medical record number, dates of birth, and dates of randomization will be kept by the RP
- f) Randomization** will be to two arms: 1g/kg/day intravenous lipid or 2 g/kg/day for 6 weeks or until develops direct bilirubin \geq 2mg/dl (in the absence of sepsis) or reaches enteral feeds and no longer requires parenteral nutrition. A block randomization with 8 subjects in each block will be performed. Study group assignments will be made by the RP with the use of a randomization scheme provided by the biostatistician. The assignment will be 1:1 ratio.

g) Route, Frequency, and Duration: The lipids will be given intravenously every day as per the standard of care for 6 weeks or until reach one of the study end points (reach enteral feeds and no longer require parenteral nutrition or has direct bilirubin ≥ 2 mg/dl in the absence of sepsis). All enrolled infants including those randomized to 2 gm/kg/day intravenous lipid will be started at 1 gm/kg/day of intravenous lipids as per the standard of care on day 2 after birth. The procedures for titrating subjects randomized to the higher dose will be consistent with standard procedures. The daily intravenous lipid intake will be increased to 2 gm/kg/day in those randomized to 2 gm/kg/day. The amount of proteins and glucose will be ordered as per the unit policy and at the discretion of the attending neonatologist.

h) Dose Adjustments: Daily assessment of the weight will be performed by the investigator and will be reported to the RP for appropriate adjustment to the dosing of the intravenous lipid. Each day, the RP will inform the clinical care team of volume of intravenous lipid to be infused over the day. The clinical care team will complete the request in the E-record using the information provided by the investigator or the RP.

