 - 2) Our hypothesis is that the development of PNAC is causally related to the cumulative lipid intake, however, protein and glucose intake may modify the association between lipid intake and PNAC. In addition, sepsis and prematurity are confounding risk factors. The sample size calculated ($n=40$) to evaluate the outcome measure (or the adverse event) accounts for the variable duration of the TPN (cumulative lipid intake) and presence of confounding risk factors. Therefore, meaningful statistical analysis is not possible with an interim analysis of less than 40 subjects.
 - 3) As suggested by our observational study, a mean cumulative dose of 55gm/kg (SD 15) of intravenous lipid is required before the development of PNAC in late preterm and term

infants. Thus, it is expected that an infant on 1gm/kg/day of intravenous lipid arm will take ~ 55 days to develop PNAC. Therefore, considering the fact that TPN intake will often be less than 42 days among study subjects, not all infants in either group are expected to develop PNAC. PNAC, the study outcome, as defined for the purpose of the study, is the earliest when any medications are used to treat PNAC as per the standard of care. Severe PNAC is defined when direct bilirubin concentration is > 10 mg/dL and is very rare. The randomization of intravenous lipid intake will be stopped long before severe PNAC may be seen among enrolled subjects.

- 4) Performing interim analyses will require more stringent significance level which will increase the sample size required to perform the study. This is a pilot study performed as part of fellow's project for which 40 subjects are required for meaningful analysis of outcome (or adverse event)
- 5) This study has been designed as a block randomization with each block having 8 subjects with 1:1 assignment, so even if all enrolled infants were to develop PNAC, it will suggest that there is no difference between the two groups and there is no causal association between intravenous lipid intake and cholestasis.

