VI. SAMPLE SIZE CALCULATION: Assuming a 4-week median follow-up time and an incidence rate of 40% for 6 weeks in control group, a two-sided log rank test with an overall sample size of 40 subjects (20 per group) achieves 80.0% power at a 0.050 significance level to detect a hazard ratio of 3.6.

Power	Incidence Rate	N Control	N Study	Haz Ratio (HR)
0.8	40%	20	20	3.6
0.8	50%	20	20	3.26
0.8	60%	20	20	3.02

Kaplan-Meier (KM) estimates of survival function will be provided and compared between groups. Log-rank test will also be used to compare time to endpoint. Cox proportional hazards model will be fitted after controlling for covariates which are found to be imbalanced in preliminary analysis. Estimate of hazard ratio and associated confidence interval will be obtained.

VII. DATA ANALYSES AND MONITORING:

a) **Randomization:** Upon successful completion of necessary screening assessments and being confirmed to be eligible by the investigator, subjects will be randomized in 1:1 ratio to two groups: 1) 1 g/kg/day intravenous lipid and 2) 2 g/kg/day intravenous lipid. Each subject will be assigned a unique sequential subject number for identification throughout the entire course of the study. The subject number will not be reused for any other participant in the study. Subjects who are discontinued or withdrawn from the study prior to randomization will be replaced. In addition, subjects who are identified to have direct hyperbilirubinemia from causes other than parenteral nutrition or did not require parenteral nutrition for more than 2 weeks will be considered screen failure and will also be replaced. We anticipate a total number of 52 subjects to participate in the study to complete the study on 40 subjects. During the study, the treatment assignments will be available only to the RP.

c) **Samples for Analysis:** The “Intent-to-Treat” sample includes all subjects who are randomized into the study. Subjects will be grouped according to the treatment to which they are randomized.

d) Statistical Analyses:

General statistical Considerations:

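### The fixed, disclosed block size of 8 could make up to 20% of assignments certain in advance, if the enrolling investigators can infer earlier arms

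*Combined protocol and SAP*

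**What the plan says.** **Allocation.** Section IV(f) says "A block randomization with 8 subjects in each block will be performed" and "The assignment will be 1:1 ratio". Section IV(m), item 5, gives the same design again: "each block having 8 subjects with 1:1 assignment". The biostatistician supplies the scheme and the research pharmacist applies it. No stratification factor is named. Recruitment is from one unit; under Section III, item 3, infants "admitted to our NICU within first 72 hours will be eligible for this study".

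**Who enrols.** Under IV(b) to IV(d) the investigators screen, approach families, assign the study number and telephone the pharmacist. Section VII(a) has subjects randomized after "being confirmed to be eligible by the investigator".

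**Who can know the arm.** Section VII(a) says: "During the study, the treatment assignments will be available only to the RP". In IV(i) the clinical team plans calories on an average lipid intake of 1.5 gm/kg/day for every enrolled infant. Against this, in IV(h) the investigator weighs the infant daily, the pharmacist tells the care team the lipid volume daily, and the care team enters the order "using the information provided by the investigator or the RP". Section V adds that daily lipid intake is collected prospectively from pharmacy and TPN records. No masking of volume, container or order is described.

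**The concern.** A pharmacist-held list conceals the next assignment only if it cannot be deduced from those already made. With a constant, published block size in a single sequence, anyone who knows the earlier arms in the current block can count what remains. Once four infants in a block have gone to one arm, every later assignment in that block is fixed.

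Here the people who might do the counting also confirm eligibility and approach families. Prognosis is partly visible at entry: the qualifying disorder is in the screening log, and the background section links cholestasis to duration of parenteral nutrition. The study team also states a directional hypothesis. Someone who knew the next arm could therefore, in principle, let that knowledge affect whether an infant is entered. Randomization would not balance such selection, and the planned Cox adjustment could correct only for covariates that were measured and found imbalanced.

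**Working it through.** **The plan's own figures.** The documents give no figure for predictability. Their only design calculation is 80.0% power (Section VI), and it reproduces:

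- Weekly control hazard: −ln(1 − 0.40)/6 = 0.0851.
- Expected events with 20 per group, 4 weeks of follow-up for all and hazard ratio 3.6: 20(1 − e^(−0.341)) + 20(1 − e^(−1.226)) = 5.8 + 14.1 = 19.9.
- Schoenfeld power: Φ(√19.9 × ln 3.6 / 2 − 1.96) = 81.5%.

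The point does not depend on this. It shows only that the design rests on about 20 events.

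**Can an arm be inferred?** Both arms use the same 20% product (IV(a)). At 0.2 g/mL, 1 gm/kg/day is 5 mL/kg/day and 2 gm/kg/day is 10 mL/kg/day. Volume divided by weight therefore separates the arms once the higher arm has been titrated up.

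**Certain assignments in a block of 8 (m = 4 per arm).** There are C(8,4) = 70 equally likely balanced blocks. Position k is forced if one arm already has 4 of the first k − 1 places, which holds in 2 × C(k − 1, 4) blocks.

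| Position | 1–4 | 5 | 6 | 7 | 8 |
|---|---|---|---|---|---|
| Blocks in which it is forced | 0 | 2 | 10 | 30 | 70 |
| Probability | 0 | 2.9% | 14.3% | 42.9% | 100% |

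The sum is (2 + 10 + 30 + 70)/70 = 112/70 = 1.6 per block, matching 2m/(m + 1) = 8/5. As a share this is 1.6/8 = 20%.

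- 40 infants (5 blocks): 5 × 1.6 = 8.0.
- 52 infants, the total anticipated in VII(a) (6 blocks plus 4 infants): 6 × 1.6 + 0 = 9.6, and 9.6/52 = 18.5%.

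**Guessing.** Always naming the arm that is behind is right m + (2^(2m)/C(2m,m) − 1)/2 = 4 + (256/70 − 1)/2 = 5.33 times in 8, or 66.6%, against 50% by chance.

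**Delay before an arm shows.** All infants start at 1 gm/kg/day and the length of titration is not stated (IV(g)). A simulation assumed Poisson accrual at 25 per year, the admission figure in Section III, item 2.

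| Assumed delay | 40 infants | 52 infants |
|---|---|---|
| 1 day | 19.2% | 17.6% |
| 3 days | 17.7% | 16.3% |
| 7 days | 14.8% | 13.8% |

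Because 25 per year counts admissions, actual enrolment would be slower and a given delay would matter less.

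**Effect of varying the block size.** This simulation of 40 infants assumed that investigators know the set of sizes and all earlier arms, but not the order of the sizes.

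| Block sizes | Certain | Best guess right |
|---|---|---|
| 8, fixed (exact) | 20.0% | 66.6% |
| 4 or 6 | 5.5% | 69.0% |
| 4, 6 or 8 | 2.4% | 67.7% |

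**The case against.** The strongest reply is that the plan says the assignments are known only to the pharmacist, and the 1.5 gm/kg/day planning figure suggests that the team was not meant to act on the arm. A reader might infer from IV(h) that the arms are openly visible to the enrolling investigators. The documents do not go that far. The investigator's stated input in IV(h) is weight and the pharmacist's is volume, and the sentence on who supplies the ordering information does not establish that investigators relay the volume. Visibility is an inference, though a close one: volume goes to the care team daily, the order is in the record, and lipid intake is study data. The planning figure hides nothing from someone who has both volume and weight.

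Inference can also be slow or wrong. Both arms start alike, and the unit policy in IV(j) of halving lipid for raised triglycerides can make an infant in the higher arm look like one in the lower arm. That stands, and it makes 20% a ceiling.

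The room for selection is limited as well. Families are to be approached as soon as possible after eligibility is established, with consent within 72 hours of birth. At 25 admissions a year (Poisson assumed), the chance of another candidate within 72 hours is 1 − e^(−25 × 3/365) = 19%, so swapping two infants is rarely possible. What remains is not enrolling an infant, or steering consent. The screening log in IV(b) and Section X records reasons for non-enrolment and the demographics of eligible infants not included, so skipped infants can be audited. It does not prevent selection.

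Finally, a fixed block is a conventional choice, and the study calls itself a pilot. That bears on the weight of the point, not on whether a cheap improvement is worth making.

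**Conclusion.** The point holds as a conditional weakness in allocation concealment. If the enrolling investigators infer earlier arms, up to 20% of assignments are certain in advance, at most about 8 of 40 infants. With 52 participants the figure is 18.5%, and with an assumed delay of 1 to 7 days it is about 15% to 19% of 40. These figures rest on a constant block of 8, a single sequence, and full knowledge of earlier arms in the block apart from the assumed delay. The plan does not say whether a replaced infant's slot is reused; reuse would add further known assignments.

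A reader might infer that selective enrolment took place, or that a few sicker infants in one arm would change the result. The documents support neither. They show an opportunity, and the size of any bias cannot be derived from them. The point is worth acting on because the change costs almost nothing and selection at entry cannot be fully repaired at analysis.

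**What to change.** 1. Have the biostatistician generate the list with randomly varying block sizes, known only to the biostatistician and the pharmacist.
2. Remove the block size from IV(f) and IV(m), item 5, in the text that investigators hold.
3. Reconcile IV(h) and Section V with VII(a): state who can see lipid volumes and daily intake during enrolment, and whether the assignment is meant to be unknown to those who enrol.

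Steps 1 and 2 remove most of the certainty, leaving about 6% (sizes 4/6) or 2% (sizes 4/6/8) even if the set of sizes leaks. They do not stop guessing, which stays near 68%; only limiting knowledge of earlier arms, the subject of step 3, would reduce that.

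The cost is one new list and a few edited sentences. The downside is a possible end-of-trial imbalance of a few infants. With sizes up to 8 the difference is at most 4, the same maximum that a fixed block of 8 already allows at 52 participants, which is 6.5 blocks. The log-rank test does not require equal groups.

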**EFFECT OF LIPID INTAKE ON DIRECT HYPERBILIRUBINEMIA IN LATE PRETERM
AND TERM INFANTS WITH GASTROINTESTINAL SURGICAL PROBLEMS**

NCT01555957

I. PURPOSE OF THE STUDY AND BACKGROUND

The purpose of the study is to establish a cause and effect relationship between lipid intake and the incidence of direct hyperbilirubinemia (cholestasis) in late preterm and term infants with major gastro-intestinal (GI) surgical disorders such as gastroschisis, omphalocele, volvulus, TE fistula, duodenal atresia, jejunal atresia, ileal atresia, Hirschsprung's disease, anorectal malformation, intestinal obstruction and GI perforations requiring surgery. Infants with major GI surgical disorders as mentioned above will be randomized to receive 1gm/kg/day or 2gm/kg/day of 20% intralipids within the first 72 hours after birth. The study is not open to all surgical infants because infants with other surgical problems can be fed enterally within few days after surgery and usually do not require TPN for prolong periods (>2 weeks). Also infants with major GI surgical disorders have similar clinical course, undergo similar type of operative procedures, and have similar complications thus eliminating potential confounding factors. The primary outcome measure is the incidence rate of parenteral nutrition associated cholestasis (PNAC). PNAC will be defined as serum direct bilirubin $\geq 2\text{mg/dl}$ in the absence of other known causes of direct hyperbilirubinemia as described under exclusion criteria.

II. BACKGROUND AND JUSTIFICATION:

Since its introduction in the late 1960s, total parenteral nutrition (TPN) has established itself as an effective mode for parenteral hyperalimentation in patients with acute or chronic intestinal failure. Out of the many complications of parenteral nutrition, the most common is the cholestasis often referred to as Parenteral Nutrition Associated Cholestasis (PNAC). PNAC is defined clinically using

direct bilirubin as an index measure in the absence of other known causes of direct hyperbilirubinemia (see exclusion criteria). The reported incidence of PNAC in neonates is as high as 84%. [1, 2]

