4. **Exclusion Criteria:** Neonates with the following condition will be excluded: 1) If does not need TPN by 72 hours; 2) Direct hyperbilirubinemia within the first 72 hours after birth; 3) TORCH infections (Toxoplasmosis, CMV, Herpes, Rubella, HIV, etc); 4) Biliary tract disorders leading to direct hyperbilirubinemia; 5) Known metabolic disorders that may be associated with direct hyperbilirubinemia- such as Galactosemia, α -1 antitrypsin deficiency, etc.

IV. METHODS AND PROCEDURES

a) Study Design: This is a prospective randomized controlled trial s planned in order to evaluate the incidence rate of PNAC between 1gm/kg/day of 20% intralipid and 2 gm/kg/day of 20% intralipid in high-risk neonates \geq 34 weeks gestational age (GA). PNAC will be defined as serum direct bilirubin \geq 2mg/dl in the absence of other known causes of direct hyperbilirubinemia as described in the exclusion criteria.

b) Screening: All neonates \geq 34 weeks GA and admitted to the NICU at URMC with major GI surgical disorders will be screened for study criteria within 72 hours after birth. Infants will be

identified by a designated investigator with regularly scheduled screening of admissions, GA, postnatal days and admission diagnosis. Screening will take place on an ongoing basis and not less than 3 times per week. The screening log will include GA, postnatal days, and type of GI surgical disorders, and whether or not the infant was enrolled in the study. If not enrolled, the reason will be recorded. The number and demographic characteristics of eligible subjects not included will be collected to assess the representation of the sample of subjects included.

- c) Enrollment and Consent:** Families will be approached by one of the investigator as soon as possible after eligibility is ascertained to allow sufficient time for the family to ask questions about the study. Parental consent may be obtained any time during the first 72 hours after birth. Consent will be documented on an IRB approved consent form. Each subject will be assigned a unique study identification number by the investigator after consent is obtained.
- d) Pre-randomization:** Once the infant is enrolled in the study, one of the investigators will notify the Research Pharmacist (RP) by telephone call during working hours (8AM-5PM) for registration and randomization. Information on weight of the infant will be provided to the RP for accurate dosing of intravenous lipid on each day.

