- k) **Primary Outcome Measures:** PNAC will be the primary outcome measure and will be defined as direct bilirubin ≥ 2 mg/dl developing within one week of the completion of 6 week randomization period in the absence of other known causes (discussed earlier). Total serum bilirubin and direct bilirubin concentration will be measured once weekly as part of the standard of care when on parenteral nutrition. The direct bilirubin is usually measured until the resolution of direct hyperbilirubinemia as part of the standard of care. If parents have consented, we will collect blood that is leftover from blood draws that are done as part of standard of care.

The blood samples will be stored in -80 degree freezer in the PI's laboratory within the Department of Neonatology for possible future research on intravenous nutrition and its effects on the liver such as identifying a more sensitive biochemical marker than direct bilirubin concentration of liver injury. Samples will be stored with a study number only and will only be linked to the data collected for the purposes of this study. Only study team members will have access to the stored blood and will be able to use the samples. Future research on stored blood after completion of this study will only be conducted by the PI on IRB approval.

- l) Secondary Outcome measures:** Secondary outcome measures will include peak direct bilirubin concentrations during hospital stay, use of choleretic medications and use of Omegavan during the hospital stay and percentage weight gain during the 6 week study period.
- m) Data Safety Monitoring:** There are several reasons why independent data safety monitoring and stopping rules were not considered for this study as described below:
 - 1) In this study, the outcome measure, direct hyperbilirubinemia $>2.0\text{mg/dL}$, is the potential side effect of interest secondary to intravenous lipid intake. As per the standard of care, the intravenous lipid intake of 1-2 gm/kg/day is routinely used in the presence of direct hyperbilirubinemia of 2 mg/dL to provide essential calories and prevent essential fatty acid deficiency. Usually, choleretic medications such as cholecystokinin are used to resolve PNAC at this point.

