Because of reasons mentioned even if the first 20 subjects (50%) hit the direct bilirubin endpoint, interim analysis is unlikely to allow meaningful analysis of the causation between lipid intake and the outcome measure (or adverse event) as provided in the protocol. In other words, it is unlikely to reach adjusted statistical significance required for interim analyses. Thus, since the outcome measure and the adverse event are the same and the sample size required to evaluate the association (or the adverse event) controlling for other factors is 40, no interim analysis and stopping rules were considered for this pilot study. For trial management, the investigation team will track enrollment and protocol compliance and review every 3 months.

V. DATA COLLECTION: The baseline data on demographics and clinical factors (antenatal and postnatal) before randomization on each subject will be collected. Similarly, data on clinical factors will be collected during the 6 week study period or until the subject is receiving intravenous lipid as per

randomization or until the subject develops PNAC (direct bilirubin ≥ 2 mg/dl in the absence of concurrent infection).

The information on TPN components, specifically amount of lipid, protein, and glucose intake on each day will be prospectively collected using pharmacy and TPN records. Information on cumulative amount of lipid intake, cumulative amount of protein intake, and cumulative amount of glucose intake will be determined for all enrolled subjects. The additional information that will be collected is duration (days) of TPN, use of trace elements, duration (days) of NPO, type of enteral feeds (maternal breast milk vs. Formula) duration (days) of antibiotic use, onset and duration of choleric medications, sepsis defined as blood culture positivity or clinical signs and symptoms of sepsis with the use of antibiotics for > 3 days, day of life when the infant reaches an enteral intake of 120 ml/kg/day, duration (days) of mechanical ventilation, duration of CPAP, duration of oxygen supplementation, and amount of erythrocyte transfusions during the study period. However, use of choleric medications and discontinuation of trace elements from the TPN is not expected during the study period based on the unit policy as delineated earlier.

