All statistical analyses will be conducted using Version 10 of the SAS System for Windows (Copyright © 2002-2003 SAS Institute Inc., Cary, NC, USA.) by a biostatistician. Descriptive statistics will be used to summarize outcomes by treatment groups. For continuous variables, descriptive statistics will include the mean, median, standard deviation, minimum, maximum, number of available observations, and number of missing observations. For discrete variables, descriptive statistics will include frequencies and percentages, number of available observations and numbers of missing observations.

We will determine whether there are important baseline differences between the two groups despite randomization with respect to participant characteristics (e.g., gender, race/ethnicity, GA at birth, SGA[<10th percentile]). If any important differences are found, the primary analyses will be repeated after statistically adjusting for these differences. If distributional assumptions associated with a particular statistical procedure are violated, appropriate transformations will be made or non-parametric alternatives will be used (e.g., Wilcoxon rank sum tests in place of two-sample t-tests). Infants enrolled but subsequently found to meet exclusion criteria will be analyzed separately.

The incidence rate of PNAC will be compared between the 2 groups using Kaplan Meier curves. Subjects who reach full enteral feeds before 6 weeks of study period will be censored. Kaplan-Meier (KM) estimates of survival function will be provided and compared between groups. Log-rank test will also be used to compare time to endpoint. Cox proportional hazards model will be fitted after controlling for covariates which are found to be imbalanced in preliminary analysis. Estimate of hazard ratio and associated confidence interval will be obtained.

The potential confounders are sepsis, use of choleric medications and trace elements. Incidence of nosocomial sepsis has decreased remarkably over the last few years in our unit and with

randomization we do not anticipate significant group differences in the incidence of sepsis. The use of choleric medications and discontinuation of trace elements should occur after the development of primary outcome as per the unit policy and therefore these factors are unlikely to confound the relationship between the lipid intake and PNAC.

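### The primary outcome window in IV(k) does not match the end point and 6-week horizon used elsewhere in the plan, and no administrative censoring day is named

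*Combined protocol and SAP*

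**What the plan says.** - **IV(k), the formal definition:** direct bilirubin ≥2 mg/dl "developing within one week of the completion of 6 week randomization period", with other known causes absent. Bilirubin is measured weekly while the infant is on PN.
- **I and IV(a):** the same threshold, "in the absence of other known causes of direct hyperbilirubinemia as described in the exclusion criteria" in the wording of IV(a), with no time window.
- **IV(f) and IV(g):** randomised lipid is "1g/kg/day intravenous lipid or 2 g/kg/day for 6 weeks or until develops direct bilirubin" ≥2 mg/dl without sepsis, or until PN is no longer needed.
- **V:** "data on clinical factors will be collected during the 6 week study period", or until randomised lipid or PNAC ends it. Sepsis is among the items collected. PNAC here means the threshold reached without concurrent infection.
- **VI:** the trial is sized on "an incidence rate of 40% for 6 weeks in control group".
- **VII(d):** "Subjects who reach full enteral feeds before 6 weeks of study period will be censored". Kaplan-Meier, log-rank and Cox analyses follow. No day is given on which infants still at risk are censored.
- **IX:** an infant at ≥2 mg/dl has reached the primary outcome and leaves randomised lipid.

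**The concern.** The formal definition is the only place where the extra week appears, and it can be read in two ways. Neither reading agrees with the rest of the plan.

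On the literal reading, the event must arise close to the end of the 6 weeks, either in a band around day 42 or in the week after it. On the other reading, one week after completion is the latest date, so anything up to day 49 counts. The first reading contradicts the sections that stop randomised lipid at the first qualifying value. The second goes beyond the period for which the plan controls lipid dose and collects the clinical data needed to rule out sepsis.

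At stake are the number of primary events in each arm and the reported incidence of PNAC. Two analysts following different sections could report different counts from the same 40 infants.

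**Working it through.** **1. Two cases, section by section**

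| First value ≥2 mg/dl | IV(k) literal | IV(k) as outer limit | IV(f), IV(g), V, IX | 6-week horizon (V, VI, VII(d)) |
|---|---|---|---|---|
| Day 20 | not an event | event | end point reached | event |
| Day 46 | event | event | randomised lipid already over | outside |

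**2. The plan's own power figure**

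Inputs from VI: 20 per group, control incidence 40% at 6 weeks, HR 3.6, two-sided 0.05, stated power 80.0%. Exponential hazards are assumed.

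- Four weeks of follow-up: events = 20(1 − 0.6^(4/6)) + 20(1 − 0.6^(3.6×4/6)) = 5.8 + 14.1 = 19.9. Schoenfeld: √(19.9/4) × ln 3.6 − 1.96 = 0.90, power 81.5%.
- Six weeks of follow-up: events = 20(0.400) + 20(0.841) = 24.8. Freedman: (2.6/4.6) × √24.8 − 1.96 = 0.86, power 80.4%.

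The figure reproduces to within 2 points. Neither calculation uses a seventh week.

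**3. What week 7 adds under the cumulative-dose figure**

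IV(m), item 3 gives a mean of 55 g/kg (SD 15) before PNAC. Assumed: a normal threshold for every infant; 1 g/kg on day 2 and the assigned dose thereafter; PN continuing to day 49; 1–2 g/kg/day in week 7 (the usual range in IX). P(event) = Φ((cumulative dose − 55)/15).

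| | 1 g/kg arm | 2 g/kg arm | Difference |
|---|---|---|---|
| Day 42 | 41 g/kg: 17.5% | 81 g/kg: 95.8% | 78 points |
| Day 49, week 7 at 1 g/kg/day | 48 g/kg: 32.0% | 88 g/kg: 98.6% | 67 points |
| Day 49, week 7 at 2 g/kg/day | 55 g/kg: 50.0% | 95 g/kg: 99.6% | 50 points |

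Week 7 adds about 15–32 points against 3–4. If no lipid is given in week 7, this model adds none.

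**4. What week 7 adds under the section VI hazards**

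The 1 g/kg arm is assumed to be control, since the HR exceeds 1.

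- Control: 1 − 0.6^(7/6) = 44.9%, against 40.0% at 6 weeks (+4.9 points).
- Other arm: 1 − 0.6^(3.6×7/6) = 88.3%, against 84.1% (+4.2 points).

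The difference goes from 44.1 to 43.4 points. The 1 g/kg share of added events is 54% here, and 63% and 71% in the 50% and 60% rows of the table in VI.

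**5. How many infants**

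IV(m) expects PN often to last under 42 days. Assume an exponential PN duration with a 4-week median: 0.5^(6/4) = 35% are still on PN at week 6.

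- Dose model, per 20: 0.354 × 20 × (0.145 to 0.325) = 1.0–2.3 added events on 1 g/kg, and 0.354 × 20 × (0.028 to 0.038) = 0.2–0.3 on 2 g/kg.
- Section VI hazards: 0.354 × 20 × (0.049 + 0.042) = about 0.6 events in total.

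In simulation with this PN duration, the crude difference under the dose model falls from about 41 to about 32–37 points.

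**6. Effect on the planned test**

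Under the dose model about 20 × 0.825 = 16.5 and 20 × 0.042 = 0.8 infants are at risk at day 42. A late 1 g/kg event therefore contributes only about −0.8/17.3 = −0.05 to observed minus expected in the 2 g/kg arm, and a late 2 g/kg event about +0.95. Simulated mean log-rank z, day 42 against day 49, with no PN censoring, is 5.7 against 5.8 (dose model) and about 3.1 against 3.3 (section VI hazards). Power under the latter goes from about 89% to 91%.

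**The case against.** The strongest reply is that the sections can be read together. Since the first value ≥2 mg/dl ends randomised lipid everywhere else, IV(k) must mean an outer limit. Section VI is then only a planning input, VII(d) says who is censored at full feeds and sets no cut-off, and V concerns clinical factors, not bilirubin. Week-7 bilirubin would exist for infants on PN, and with weekly sampling a grace week picks up PNAC that arose in week 6.

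Much of this stands. The outer-limit reading is the likelier intention, and nothing in the plan shows an intent to discard early events, so a reader should not infer that. The sampling argument is a fair reason for wanting the extra week. But this reading leaves the cut-off unstated in the analysis section and carries the outcome a week past the planned collection of sepsis data, although IV(f) and IV(g) make absence of sepsis part of the end point.

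Three further inferences are tempting and not supported:

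- *Almost all added events fall in the 1 g/kg arm.* That holds only under the dose model (85–93% across titration and week-7 dose assumptions). The section VI hazards give 54–71%.
- *The extra week pulls the trial's comparison towards no difference.* Under the dose model the incidence difference shrinks, but the planned log-rank statistic does not.
- *Week-7 events occur on non-randomised lipid.* Randomised dosing is over by then, but no section says what lipid an infant without PNAC receives after week 6; IX covers only infants who have reached the outcome.

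**Conclusion.** The contradiction holds on the text alone and needs no model: the status of a day-20 or a day-46 value depends on the section followed, and the analysis plan has no administrative censoring day. It concerns the primary outcome and should be settled before analysis.

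Its size is modest and model-dependent. Reported incidence could move materially under the dose model if many infants stayed on PN, and hardly at all under the section VI hazards. With a 4-week median PN duration (assumed), about one to three infants in the trial would change status under the dose model, and fewer than one under section VI. The log-rank conclusion is essentially unaffected. These figures rest on the assumed normal threshold, continued PN and lipid in week 7, and 1 g/kg as the control arm. The documents state none of these.

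**What to change.** Use one definition in I, IV(a), IV(k), V and VII(d): *first direct bilirubin ≥2 mg/dl after randomisation and up to the end of the 6-week study period, in the absence of other known causes and of sepsis*. Both qualifiers must stay, because sepsis is not on the exclusion list to which I and IV(a) refer.

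In VII(d), state administrative censoring at day 42 for the Kaplan-Meier, log-rank and Cox analyses, and name the day from which the 42 days are counted. The existing rule for full enteral feeds continues to apply before then.

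Report values from days 42–49 as a separate sensitivity count by arm, with the lipid actually received and sepsis status in that week. Section V would need one line extending data collection to support this.

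The cost is wording, one extra week of limited data for infants still on PN, and the loss from the primary count of a few week-7 detections, some of which may reflect onset in week 6.
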